9.1. Extent of Exposure

A listing of exposure data will be a by-subject listing including the cohort, treatment administered with the dates and times of treatment administration.

9.2. Adverse Events

All adverse events (AEs) will be coded and classified according to system organ class, high level term, and preferred term using GSK MedDRA. All AEs will be listed. A listing of subject numbers for individual AEs will also be prepared. A summary, overall and by treatment, of the number and percent of subjects reporting each event at least once will be generated for all AEs and also for drug-related AEs. A listing of the relationship of AE body systems, group terms and verbatim text will also be produced.

9.3. Deaths and Serious Adverse Events

In addition to the listing described above, deaths and serious AEs (SAEs), if they occur, will also be listed and summarized separately.

9.4. Adverse Events Leading to Discontinuation of Investigational Product and/or Withdrawal from the Study and Other Significant Adverse Events

If any subject withdraws due to an AE, then a listing and a summary by treatment will be provided for these subject(s).

9.5. Clinical Laboratory Evaluations

A listing for hematology and clinical chemistry values of potential clinical importance as described in Section 7.6, will be produced where applicable.

For hematology and clinical chemistry data, descriptive summaries for actual values by time point will be produced. A summary of urinalysis dipstick data and a listing of urinalysis data will be produced.

9.6. Vital Signs and Body Weight

Listing of vital signs values of potential clinical importance as described in Section 7.6, will be produced where applicable. Descriptive summaries for absolute and change from baseline values for vital signs by time point will be produced.

9.7. Electrocardiograms

Descriptive summaries for absolute and change from baseline values of ECG values by time point will be produced.

ECG findings will be summarized with the highest (worst) severity across replicated assessments at the specified time point used.

ECG abnormalities of clinical significance, if they occur, will be listed for each subject.

10. PHARMACOKINETIC ANALYSES

The reconciliation of the PK Case Report Form (CRF) and SMS2000 data will be performed by, or under the direct auspices of, Clinical Pharmacology Data Sciences (CPDS), GlaxoSmithKline.

The merge of PK concentration data, randomisation and CRF data will be performed by, or under the direct auspices of, QSI (Programmer), GlaxoSmithKline.

Derivation of pharmacokinetic parameters will be performed by, or under the direct auspices of, Clinical Pharmacology Modelling and Simulation (CPMS), GlaxoSmithKline.

Statistical analysis of pharmacokinetic parameters will be performed by, or under the direct auspices of, Clinical Statistics, GlaxoSmithKline.

The precise format and content of PK tables, figures, and listings are shown in Section 14.1.3 and Section 14.1.6 of the RAP.

10.1. Drug Concentration Measures

Concentrations of GSK1278863 and its metabolites (GSK2391220 (M2), GSK2506104 (M3), GSK2487818 (M4), GSK2506102 (M5), GSK2531398 (M6), GSK2531401 (M13)) in plasma will be listed and summarized by cohort (i.e., CAPD, APD and both combined) and nominal time. Standard summary statistics will be calculated (i.e. mean, standard deviation, median, minimum and maximum). Refer to the PK Guidance document, GUI_51487 (3.0), for more information regarding the treatment of plasma concentrations below the assay's lower limit of quantification (NQ).

Individual plasma concentration-time profiles and median/mean profiles by treatment cohort will be plotted. Each of the figures will contain one plot on the untransformed scale (i.e. a linear plot) and one plot on the log transformed scale (i.e. log-linear plot). See Section 14.1.3 and Section 14.1.5 Pharmacokinetic Source Figures and Tables for details.

GSK1278863 and metabolite protein binding (as a percentage) will be presented in tabular form and will be summarized descriptively. Metabolite-to-parent exposure ratios (corrected for molecular weight) will also be calculated and summarized descriptively.

Volume of drained dialysate plus concentrations and amounts of GSK1278863 and its metabolites (GSK2391220(M2), GSK2506104 (M3), GSK2487818 (M4), GSK2506102 (M5), GSK2531398 (M6), GSK2531401 (M13)) in the dialysate will be listed and summarized by cohort (i.e., CAPD, APD and both combined).

10.2. Deriving and Summarizing Pharmacokinetic Parameters

From the plasma concentration-time data of parent GSK1278863 and metabolites (GSK2391220 (M2), GSK2506104 (M3), GSK2487818 (M4), GSK2506102 (M5), GSK2531398 (M6) and GSK2531401 (M13)), the following pharmacokinetic parameters will be determined, as data permit:

Day 1: Maximum observed plasma concentration (C_{max}), time to C_{max} (t_{max}), area under the plasma concentration-time curve AUC(0-τ) and AUC(0-∞), and apparent terminal phase half-life (t_{1/2}).

Day 14: C_{max}, t_{max}, AUC(0-τ), and apparent terminal phase half-life (t_{1/2}). AUC(0-∞), AUC(0-τ), and C_{max} following single (Day 1) and repeat doses (Day 14) will be used for determination of accumulation and time-invariance ratios.

Day 12 to 15: Trough concentration (C_{tau}, or C_τ) samples collected on Days 12 to 15 will be used to assess attainment of steady state.

- Note, to comply with CDISC reporting requirements, the following parameters also will be determined:
 - T_{last}
 - Where t_{1/2} and/or AUC(0-∞) have been derived the following parameters should also be included in the PKPAR file: No_points_lambda_z, Lambda_z_lower, Lambda_z_upper, T_{last}
 - If partial areas have been calculated, the following parameters should also be reported (if not included as above): No_points_lambda_z, Lambda_z_lower, Lambda_z_upper

Other Plasma PK Analyses: GSK1278863 and select metabolite (GSK2487818 (M4), GSK2506102 (M5)) unbound concentration and free fraction (as a percentage) will be presented in tabular form and will be summarized descriptively. Metabolite-to-parent exposure ratios (corrected for molecular weight) will also be calculated and summarized descriptively.

- **Percent protein bound will be calculated using the formula:**

$$\% \text{ Bound} = \frac{(\text{Concentration in plasma} - \text{Concentration in ultrafiltrate}) * 100}{\text{Concentration in plasma}}$$

- **% Metabolite to parent ratios:** (GSK2391220(M2), GSK2506104 (M3), GSK2487818 (M4), GSK2506102 (M5), GSK2531398 (M6) and GSK2531401 (M13)) (metabolites, M) to GSK1278863 (parent) AUC and C_{max} ratios will be determined (as a percentage, including a correction for molecular weight, Mr), for example:

$$M : \text{GSK1278863} \% = 100 * \left(\frac{\text{AUC}_M}{\text{AUC}_{\text{GSK1278863}}} \right) * \left(\frac{\text{Mr}_{\text{GSK1278863}}}{\text{Mr}_M} \right)$$

Parameters to be used in this calculation are:

Day 1: C_{max}, AUC(0-τ), AUC(0-∞)

Day 14: C_{max}, AUC(0-τ)

- Molecular weights for compounds are:

Compound	Molecular Weight (g/mol)
GSK1278863	393.442
GSK2391220 (M2)	425.442
GSK2506104 (M3)	425.442
GSK2487818 (M4)	425.442
GSK2506102 (M5)	425.442
GSK2531398 (M6)	425.442
GSK2531401 (M13)	441.442

- Percent drug related material (%DRM):** will be determined for parent as well as each metabolite, where the denominator is the sum of the exposures of all analytes. Where all these AUCs are corrected for molecular weight (Mr).

Example:

$$\%DRM_{GSK1278863} = 100 * AUC_{GSK1278863} / (AUC_{GSK1278863} + AUC_{M2} + AUC_{M3} + AUC_{M4} + AUC_{M5} + AUC_{M6} + AUC_{M13})$$

Parameters to be used in this calculation are:

Day 1: AUC(0-τ), AUC(0-∞)

Day 14: AUC(0-τ)

- Peritoneal dialysis clearance of GSK1278863 and metabolites will be calculated from Day 14 dialysate excretion data as total amount of analyte excreted over 24 h divided by plasma AUC(0-τ).

$$CL_d = Ae(0-\tau) / AUC(0-\tau)$$

where Ae is the amount of analyte excreted in dialysate over the 24 h dialysate collection period

$$Ae = \text{total dialysate volume} * \text{dialysate concentration}$$

All the derived parameters described above will be listed. For each of these parameters, except t_{max}, the following summary statistics will be calculated for each cohort (CAPD, APD and combined) as well as different peritoneal dialysis solution (number of categories to be determined) : median, maximum, minimum, arithmetic mean, standard deviation, coefficient of variation, geometric mean, 95% confidence interval for the

geometric mean and standard deviation of logarithmically transformed data. For t_{\max} , median, maximum, minimum, arithmetic mean and standard deviation will be calculated. The first point, last point and number of points used in the determination of λ_z will be included on the listing of the derived parameters.

10.3. Statistical Analyses

Descriptive statistics (n, arithmetic mean and associated 95% confidence interval, standard deviation, minimum, median, maximum) will be calculated for all pharmacokinetic endpoints of GSK1278863 and metabolites by Cohort. In addition geometric means, associated 90% CIs, and estimates of between-subject CVs (CVb (%)), will be calculated for each Cohort where

Geometric mean = $\exp(\text{mean on } \log_e \text{ scale})$

CVb (%) = $\text{SQRT}(\exp(\text{SD}^2) - 1) \times 100$, where SD is the standard deviation of the \log_e -transformed data.

Steady State Assessment

Trough concentration (C_{τ}) samples collected on the specified days (Days 12, 13, 14, and the 24 h post-dose sample on Day 14) will be used to assess attainment of steady state. Individual trough concentration data C_{τ} will be plotted and listed. C_{τ} will be summarized by day and cohort, and the mean and median plots will be provided.

Steady state will be assessed separately for GSK1278863 and metabolites in each cohort.

A linear mixed effects ANOVA model will be used to evaluate steady state for GSK1278863 and each metabolite. The dependent variable will be log-transformed Predose (trough) concentrations (C_{τ}) on Days 12 to 15. Independent variables in the model include day (as a continuous variable) as a fixed effect and subject as a random effect.

Assessment of plasma GSK1278863 and metabolites steady state will be assessed by evaluating the estimated slope for the day parameter and associated 90% CI for both the cohorts combined. A steady state attainment is defined as the 90% confidence interval of the slope including 0.

Secondary Comparisons:

Assessment of Accumulation

To estimate the extent of accumulation for GSK1278863 and metabolites after repeat dosing, the observed accumulation ratio R_0 will be determined.

$$R_0 = \frac{AUC(0-\tau)_{ss}}{AUC(0-\tau)}$$

Where $AUC(0-\tau)_{ss}$ is AUC from time zero to t h under steady state and $AUC(0-\tau)$ is AUC from time zero to dosing interval at Day 1.

To evaluate the accumulation ratio, statistical analysis of GSK1278863 and metabolite PK data for each cohort will be performed separately after a log transformation of the data.

A mixed effect model will be fitted with day (single and repeat dose), as fixed effects and subject as a random effect. Day 14 will be compared to Day 1 in order to estimate the accumulation ratios, $R_0 = (AUC(0-\tau, \text{Day14}) : AUC(0-\tau, \text{Day1}))$. The ratios will be calculated by back-transforming the difference between the LS means.

Using the pooled estimate of variance, 90% confidence intervals will be calculated for the primary comparisons, and back-transformed to the original scale.

Assessment of Time Invariance

To evaluate the time invariance ratio, statistical analysis of $(AUC(0-\infty) \text{ Day 1})$ and $AUC(0-\tau) \text{ (Day14)}$, of GSK1278863 and metabolites for each cohort will be performed separately after a log transformation of the data.

A mixed effect model will be fitted with day as a fixed effect and subject as a random effect. Day 14 $AUC(0-\tau)$ will be compared to Day 1 $AUC(0-\infty)$ in order to estimate the time invariance ratios, $RS = (AUC(0-\tau, \text{Day 14}) : AUC(0-\infty, \text{Day 1}))$. The ratios will be calculated by back-transforming the difference between the LS means.

Using the pooled estimate of variance, 90% confidence intervals will be calculated for the primary comparisons, and back-transformed to the original scale.

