*In vitro* pharmacology has shown that all major metabolites of GSK1278863 are pharmacologically active and show  $pIC_{50s} > 8$  (<10 nM), comparable to the parent compound GSK1278863 for human prolyl -4- hydroxylases (PHDs). Therefore, there is the potential that the metabolites also may contribute to the clinical pharmacodynamics (PD) and therapeutic activity of GSK1278863. While a previous clinical study of GSK1278863 in subjects with impaired renal function had demonstrated that parent GSK1278863 has similar pharmacokinetic characteristics to subjects with normal renal function (Study PHI112843). Preliminary PK data suggests that the major metabolites of GSK1278863 have prolonged half-lives compared to parent GSK1278863, with some metabolites accumulating upon repeat-dose administration in subjects with chronic kidney disease (CKD; Study PHI115573). Full PK profiles of GSK1278863 and metabolites have not been collected following repeat-dose administration to the ESRD population undergoing peritoneal dialysis; therefore, the purpose of this study is to fully characterize the PK of GSK1278863 and metabolites following repeat-dose administration to this population. This open-label study will evaluate the PK of parent

GSK1278863 and metabolites in two cohorts of ESRD subjects undergoing peritoneal dialysis.

The effective date of the original protocol is 11-APR-2014. In the 2 years that the study has been active, only 6 subjects have completed the study. This includes 1 CAPD and 5 APD subjects. Considering the difficulties with recruitment in general, and the CAPD population in particular, this protocol will be amended to enroll ESRD subjects undergoing peritoneal dialysis of either modality (i.e., CAPD or APD). In addition, in a previous study (PHI115573), the pharmacokinetic properties of daprodustat and the predominant metabolites were able to be adequately characterized in an ESRD population undergoing hemodialysis with 8 subjects. Finally, preliminary results from this study has shown that a subject using CAPD had similar PK to the 3 subjects using APD suggesting that, if there are differences in the PK of daprodustat depending upon the peritoneal dialysis modality, they are likely to be not considered clinically significant.

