### **3.2. Discussion of Study Design**

The purpose of this study is to characterize the pharmacokinetics of GSK1278863 and metabolites in ESRD patients undergoing peritoneal dialysis. To date, GSK1278863 has not been administered to this patient population, and there have been differences in the PK of the metabolites in subjects with CKD (Stage 3/4), both in subjects not on dialysis as well as in subjects undergoing hemodialysis, as compared to subjects with normal renal function.

In this study, subjects will receive GSK1278863 for 14 days. Steady-state parent and metabolite PK have been evaluated after repeat-dose administration of 5 mg GSK1278863 in healthy subjects and subjects with renal impairment (Stage 3/4 NDD and Stage 5 HDD) in Study PHI115573. PK of parent GSK1278863 was generally similar across healthy, NDD, and HDD subjects; slightly (16%) higher AUC was observed in HDD subjects on a dialysis day (GSK1278863 dosed ~2 h prior to dialysis) compared to a non dialysis day.

Compared to healthy subjects, steady-state metabolite exposures were 2.3 to 3.6-fold higher in NDD subjects, 1.8 to 3.3-fold higher in HDD subjects on a dialysis day, and 3.0 to 6.9-fold higher in HDD subjects on a non-dialysis day.

In HDD subjects, metabolites demonstrated 1.7 to 2.3-fold higher exposure on a non-dialysis day compared to a dialysis day. Metabolite PK reached steady-state by 14 days.

Since no placebo treatment group is required in this PK study, an open-label study design will be used.

Plasma biomarker concentrations of on-target effects (erythropoietin and hepcidin) will be obtained to examine the time course of changes in erythropoietin and hepcidin after a 5 mg dose.

Samples for assessment of steady-state plasma protein binding will be collected (3 samples to obtain approximate peak and trough concentrations of GSK1278863 and metabolites, M4 (GSK2487818) and M5 (GSK2506102). Samples (aliquots) from the

peritoneal dialysis fluid (dialysate) will be collected for determination of clearance of GSK1278863 and metabolites at steady-state on Day 14.

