#### Steady State Assessment

Trough concentration ( $C_{\tau}$ ) samples collected on the specified days will be used to assess attainment of steady state. Individual trough concentration data  $C_{\tau}$  will be plotted and

listed.  $C\tau$  will be summarized by day and cohort, and the mean and median plots will be provided.

Steady state will be assessed separately for GSK1278863 and metabolites in each cohort.

A linear mixed effects ANOVA model will be used to evaluate steady state for GSK1278863 and each metabolite. The dependent variable will be log-transformed pre-dose (trough) concentrations ( $C\tau$ ) on Days 12 to 15. Independent variables in the model include day (as a continuous variable) as a fixed effect and subject as a random effect.

Assessment of plasma GSK1278863 and metabolites steady state will be assessed by evaluating the estimated slope for the day parameter and associated 90% CI for both the cohorts combined.

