6. HYPOTHESES AND TREATMENT COMPARISONS

Precision Estimation

This study is designed to estimate pharmacokinetic endpoints of GSK1278863 and metabolites in ESRD patients undergoing peritoneal dialysis following repeat administration of 5 mg once daily GSK1278863.

There will be two cohorts of subjects in this study: subjects with CAPD and subjects with APD.

No formal statistical hypotheses will be tested. An estimation approach will be used to evaluate the comparisons of interest, with point estimates and associated 90% confidence intervals presented to provide a range of plausible values for the comparisons.

Table 1 Treatment and Other Sub-Group Descriptions for Data Displays

Randomisation		Final Data Display (i.e. HARP / other)
Treatment	Cohort Description	Cohort
5 mg GSK1278863	Continuous Ambulatory Peritoneal Dialysis	CAPD
	Automated Peritoneal Dialysis	APD

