8. STUDY POPULATION

It was initially expected that 30 subjects (15 in each cohort) would be needed to be recruited in order to ensure that at least 12 subjects (6 in each cohort) completed the trial. However, during the informal review of the available PK data it was determined that there were no clinically-significant differences in PK between the CAPD/APD and CKD populations, therefore the planned number of subjects was reduced to enrol 7 subjects and 5 subjects completed the study in order to minimize unnecessary additional subject exposure.

Study population data will be summarised by, or under the direct auspices of, Clinical Statistics, GlaxoSmithKline.

The precise format and content of Study Population tables and listings are shown in Section 14.1.1 and Section 14.1.5 of the RAP.

The tables will use the “All Subjects” population unless otherwise specified.

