14.2. Data Display Specifications (Example Shells)

Example : *Exhibit 1*
Protocol : *200942*
Population : *PK Population*

Page 1 of n

Table xx.x
Summary of Results of Statistical Analysis to Assess Steady state

Day	Back-Transformed Slope	90% Confidence Interval
1-14	1.05	(1.03, 1.08)

Example : *Exhibit 2*
Protocol : *200942*
Population : *PK Population*

Table x.x
Summary of Results of Statistical Analysis to Estimate Accumulation Ratio

Parameter	Comparison	Geom.LsMean		Ratio	90% Confidence Interval
		n	Test		
AUC (0-t) (pg*hr/mL)	Day 14 vs Day 1	12	0.910	12 0.780	1.166 (0.843, 0.978)

Example : *Exhibit3*
 Protocol : *200942*
 Population : *PK Population*

Page 1 of n

Table x.x
 Summary of Results of Statistical Analysis to Estimate Time Invariance

Comparison	Geom.LsMean		Ratio	90% Confidence Interval		
	n	Test			n	Ref
AUC (0- τ) Day 14 vs AUC (0- ∞) Day 1	12	0.910	12	0.780	1.166	(0.843, 0.978)

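### The SAP counts a trough-slope 90% CI that includes zero as proof of steady state, so with 5 to 8 subjects imprecision becomes a positive verdict

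*SAP*

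**What the plan says.** In the steady-state part of SAP section 10.3, log trough concentrations from "Days 12, 13, 14, and the 24 h post-dose sample on Day 14" are regressed on day as a continuous variable, with subject as a random effect, for the parent and each metabolite. The SAP then gives a criterion: "A steady state attainment is defined as the 90% confidence interval of the slope including 0". No margin accompanies it.

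Protocol section 9.3.2.3.1 has the same model and says that steady state is assessed by "evaluating the estimated slope for the day parameter and associated 90% CI for both the cohorts combined". It gives no pass/fail rule. SAP section 6 states that "No formal statistical hypotheses will be tested" and that estimation will be used.

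On numbers, Protocol section 3.1 plans 8 completers. SAP section 8 says that "the planned number of subjects was reduced to enrol 7 subjects and 5 subjects completed the study".

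The results shell, Exhibit 1 in SAP section 14.2, has a column headed "Back-Transformed Slope" and labels the row as Days 1-14.

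**The concern.** A 90% CI that includes zero means only that a zero slope was not rejected at the two-sided 10% level. It does not show that the slope is small. Because the rule has no margin, a wide interval passes more easily than a narrow one, so less information favours the desired conclusion. It also errs the other way: a trivial slope estimated very precisely would be called not at steady state.

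The primary objective is the steady-state PK of the parent and six metabolites. Protocol section 1.1.1 says that the metabolites have prolonged half-lives, "with some metabolites accumulating upon repeat-dose administration in subjects with chronic kidney disease". What is at stake is the steady-state conclusion for each of seven analytes in a population in which full repeat-dose profiles had not been collected, and hence how the Day 14 values are read.

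**Working it through.** **Plan's own figure.** Neither document gives a precision for the trough slope. The only current precision figure (Protocol 9.2.1) is a 90% CI half-width within 56% for 8 subjects at a CV of about 50%. With log-scale SD √ln(1+0.5²) = 0.472, exp(t₀.₉₅,₇ × 0.472 × √(2/8)) − 1 = 56.4%, so it is reproduced as a paired contrast. It concerns PK parameters and says nothing about the slope.

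**Inputs from the documents.** Four consecutive daily troughs per subject, cohorts combined, random intercept, 90% CI. Number of subjects n = 5 (SAP section 8) to 8 (Protocol section 3.1).

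**Assumptions.** The documents give no within-subject trough CV (range used: 5% to 50%) and no metabolite half-life in peritoneal dialysis (5 days used, with 3 days and no elimination for comparison). Accumulation is linear, dosing is once daily and data are complete.

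**Size of the rise.** Troughs on Days 12 to 15 follow d = 11, 12, 13 and 14 doses, so C is proportional to 1 − exp(−ln2 × d / t½).

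- t½ = 5 days: 78.2% of plateau on Day 12 and 85.6% on Day 15. Fitted log slope 0.0301, so exp(slope) = 1.031 per day; Day 15/Day 12 = 1.095.
- t½ = 3 days: 1.014 per day, 96% of plateau on Day 15.
- No elimination (the largest possible rise): troughs in the proportions 11:12:13:14, 1.084 per day, Day 15/Day 12 = 1.27.

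**Precision of the slope.** The sum of squares of day about its mean is 1.5² + 0.5² + 0.5² + 1.5² = 5 per subject. Then SE = s_w/√(5n), with s_w = √ln(1+CV²) and 3n − 1 degrees of freedom. At CV 20%, s_w = 0.198:

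- n = 5: SE = 0.0396, t₀.₉₅,₁₄ = 1.761, half-width 0.0698. This is a factor of 1.072 per day and exp(3 × 0.0698) = 1.23 over Days 12 to 15.
- n = 8: SE = 0.0313, t₀.₉₅,₂₃ = 1.714, half-width 0.0537. This is a factor of 1.055 per day and exp(3 × 0.0537) = 1.17 over Days 12 to 15.

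**Probability that the rule declares steady state.** This is the chance that the 90% CI includes zero, from the noncentral t with noncentrality slope/SE:

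| True state | n | CV 5% | CV 10% | CV 20% | CV 50% |
|---|---|---|---|---|---|
| Flat | any | 90% | 90% | 90% | 90% |
| t½ 5 days | 5 | 11% | 58% | 81% | 88% |
| t½ 5 days | 8 | 2% | 42% | 76% | 87% |
| No elimination | 5 | 0% | 1% | 39% | 79% |
| No elimination | 8 | 0% | 0% | 20% | 72% |

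For the 5-day half-life and CVs from 20% upward, the pass rate lies only 90 − 81 = 9 down to 90 − 88 = 2 points below that of a flat analyte at n = 5, and 90 − 76 = 14 down to 90 − 87 = 3 points below at n = 8.

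**Shell.** A back-transformed slope is always positive, so its interval can never include 0; its no-change value is 1. The Days 1-14 label does not match the Days 12 to 15 model.

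**The case against.** The strongest objection concerns size. For an analyte with a 5-day half-life each trough averages many doses, so its within-subject CV may well be below 20%; the 50% in Protocol 9.2.1 describes PK parameters and not repeat troughs within a subject. A one-compartment simulation with 20-50% dose-to-dose input variation and 5-10% assay error gave residual log SDs of 0.06 to 0.12. The rule then passed 22-65% of trials at n = 5 and 7-53% at n = 8. Day-to-day variation in clearance was left out and would raise these figures. This stands as a reason to give the low-CV columns equal weight. It does not rescue a rule that may pass a rising analyte about half the time.

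Second, Protocol section 3.2 says of the earlier study in healthy, non-dialysis and hemodialysis subjects that "Metabolite PK reached steady-state by 14 days". Large rises are therefore unlikely, and at a 3-day half-life a pass would mislead little. But that study had no peritoneal dialysis subjects, and a reassuring prior does not justify the rule.

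Third, the slope, its CI and the trough plots are reported anyway, so a reader can see the imprecision, and no primary estimate depends on the verdict. That is correct and limits the harm.

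Fourth, deleting the rule leaves no yes/no criterion. That is also correct, but a margin would rarely help here: with an assumed band of ±10% per day, a truly flat analyte at CV 20% would satisfy it in only 48% of trials at n = 5 (81% at n = 8).

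Finally, Exhibit 1 holds dummy values, and a log-slope CI including 0 is equivalent to a back-transformed CI including 1. The shell is a labelling matter only.

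**Conclusion.** The concern holds. The attainment definition appears only in the SAP, goes beyond the protocol's estimation approach, and rewards imprecision. Its practical effect depends on trough variability, which the documents do not give: at a within-subject CV of 5% the rule detects the illustrated rise well, at 10% it passes roughly half of trials, and from 20% upward it hardly separates a rising analyte from a flat one. These figures also rest on the assumed 5-day half-life, linear accumulation and complete data. The logical fault does not rest on them. The model is sound and the estimates of AUC, Cmax, accumulation and time invariance are unaffected. The text should be corrected because the steady-state statement for each analyte could otherwise be unsupported.

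**What to change.** In SAP section 10.3, delete the sentence that defines attainment. For each analyte, report exp(slope) per day with its 90% CI (no change = 1), and the implied Day 12 to Day 15 ratio, exp(3 × slope), with its 90% CI. Add that steady state will not be declared merely because the interval includes no change; instead the report states the largest rise that the interval does not exclude, beside the trough plots already planned. In Exhibit 1, relabel the row as Days 12-15 and give the reference value as 1. No equivalence band is proposed.

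The cost is one SAP sentence replaced and one shell relabelled, with the same model and data. The price is the loss of a simple yes/no statement for each analyte, and the report will have to show how wide the intervals are: at a CV of 20%, a factor of about 1.23 either way for the Day 12 to Day 15 ratio with 5 subjects, or 1.17 with 8.
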